The same tables may be used to judge the precision of the comparison between homosexual/bisexuals and IV drug users relative to the PCP as set forth in Question 6. Table 3.3 indicates that a difference of .04 at the end of one year of follow-up would be judged significant for the comparison of homosexual/bisexuals versus IV drug users.

Tables 3.4 through 3.6 are relevant in answering questions about the precision of comparisons in Question 10. Tables 3.4-3.6 deal with the precision of comparisons in DLCO. Groups A, B and C are of interest in these tables. A standard deviation of 2.5 is used for the DLCO calculations. According to Question 10, the primary comparisons of interest are Group A versus Group C and Group B versus Group C; these

comparisons being made within risk categories. This being the case, it is seen that the respective comparisons for DLC0 in IV drug users would be declared significant if the difference were greater than 0.8 and would be declared significant for the homosexual/bisexual comparisons if differences greater than 0.5 were observed.

Finally, Tables 3.7 through 3.10 show precision estimates for long-term mortality estimates and comparisons. In terms of Question 13, the comparison of interest is between the "intensively" screened and the "routinely" screened groups. For the overall long term mortality comparisons between the two groups, a mortality difference of 6% would be judged significant at the end of the study with this design.

Precision Estimates for
PCP Incidence Estimates and Comparisons*

Table 3.1

1/2 Confidence Intervals for Incidence

	A	B	C	Total
H/BS	0.02	0.04	0	0.02
IV	0.04	0.07	0	0.03
OTH	0.07	0.13	0	0.08
TOT	0.02	0.03	0	

Table 3.2

1/2 Confidence Intervals (Comparisons)

	AvsB	AvsC	BvsC
H/BS	0.05	0.02	0.04
IV	0.08	0.04	0.07
OTH	0.15
TOT	0.04	0.02	0.03

Table 3.3

1/2 Confidence Intervals (Comparisons)

	A	B	C	Total
H/BSvsIV	0.04	0.08	0	0.04
H/BSvsOTH	0.08	0.14	.	0.08
IVvsOTH	0.08	0.15	.	0.08

* Assumption for calculations were: After one year of follow-up,
Prevalence in A = 5%
Prevalence in B = 20%
Prevalence in C = 0%. (Source: Moss et al., Brit. Med. J., 1987; 1)

Precision Estimates for Comparison of DLCO
Among Disease and Transmission Groups****

Table 3.4

1/2 Confidence Intervals

	A	B	C	Total
H/BS	0.8	0.8	1.0	0.5
IV	1.0	1.0	1.8	0.8
OTH	2.0	2.0	...	1.5
TOT	0.5	0.5	1.0	

Table 3.5

1/2 Confidence Intervals (Comparisons)

	AvsB	AvsC	BvsC
H/BS	1.0	1.3	1.3
IV	1.5	2.0	2.0
OTH	3.0
TOT	0.8	1.0	1.0

Table 3.6

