there may be pulmonary involvement, either primary or secondary, at any point in the course of HIV disease. Although much is known about the pulmonary disorders associated with AIDS, there are very important deficiencies in the available information. These deficiencies are due in large part to clinicians and investigators focusing on those disorders that serve to define AIDS or that occur in patients who have AIDS. There is little or no information that systematically identifies the pulmonary disorders that occur at all stages of HIV disease or that describes the course patients follow after the diagnosis of a lung disease has been established.

2. Primary and Secondary Objectives

The primary objective of this study is to determine the prevalence, incidence, and types of lung diseases that occur in persons in selected HIV transmission categories with and without HIV infection and to describe the course and outcome of these disorders.

Within the context of the primary objective there are several secondary objectives that this study seeks to achieve. These are subsidiary to the primary objective but have importance in their own right.

The secondary objectives are as follows:

1. To identify demographic, clinical, and immunologic and other laboratory variables that are associated with the subsequent diagnosis of specific HIV-related lung diseases;
2. To describe the clinical, radiographic, and pulmonary physiologic, immunologic, and other laboratory variables that are associated with specific HIV-related lung diseases at the time the disease is diagnosed;
3. To determine if there is a difference in the prevalence/incidence of identified pulmonary disease, respiratory symptoms, chest radiographic abnormalities, and rates of decline in pulmonary function in subjects with HIV infection compared with these same variables in subjects from the same HIV transmission categories who do not have HIV infection;

4. To measure the frequency with which HIV-related lung diseases are present in HIV-infected persons who do not have symptoms;
5. To compare survival, days in hospital and functional status in subjects who have had lung diseases diagnosed as a result of intensive screening or evaluation of respiratory symptoms with subjects who have had the same diseases diagnosed as a result of routine screening tests or evaluation of respiratory symptoms.

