table analyses of 2 or higher dimensions will be constructed to assess statistically whether or not the different pulmonary diseases tend to occur together or whether they are basically independent. Chi-square tests for association will be appropriate in this situation. Simple adjustment for single confounding variables may be made by Mantel-Haenzel methods and more complicated adjustments will be done by loglinear modelling.

Question 12 is, "Does diagnosis of P. carinii pneumonia by intensive screening decrease both short-and long-term mortality?" All seropositive patients will be included in this analysis and the major comparison of interest will be the intensively screened patients versus those who have been randomized to routine evaluations. Since this is a randomized substudy, there is much less concern about selection bias than for the other questions of interest which involved nonequivalent groups. In this case the principal predictive variable of interest is intensive or routine screening and the outcome is short and long term mortality. Variables confounding the interpretation of the analysis include various forms of treatment which patient may be on. To explore question 12, Kaplan Meier survival curves (or Cox regression if covariables must be dealt with) will be computed and statistically compared. In the calculation of the curves it will be important to take the origins of the survival curve as the time of randomization in order to avoid length biased sampling. Additionally, based on back extrapolation of the slope of decline of CD-4 cell counts the approximate time of HIV infection can be estimated and used as the starting point for the curves.

If the answer to question 12 is "No", one may well wish to investigate the reasons for the lack of impact of the intensive effort. A logical inquiry in this regard is whether or not the lead time between onset of preclinical disease and symptoms is sufficient to permit a significant alteration of the disease process. In this regard, extensions to methodology of Zelen and Feinleib, [Biometrika, 1969, pp.601-614] may be useful in estimating the lead time from incidence and prevalence data from the intensive and routine study arms.

10. Quality Control

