Presence of specific HIV-related lung diseases (Appendix 2)

Absence of specific HIV-related lung diseases. Determined by lack of findings on evaluations as specified in Section 7.2.4 or by clinical course during one month following the evaluation

Analysis

Calculation of sensitivity. Regression models will be used to adjust for confounding variables.

Question 12. Does diagnosis of *P. carinii* pneumonia by intensive screening decrease both short- and long-term mortality?

Groups studied

All HIV seropositive subjects

Predictive variables

Diagnosis by intensive or routine screening or by symptom evaluation

Confounding variables

Treatment regimens for *P. carinii* pneumonia

Coexisting diseases

Antiviral therapy

Preventive therapy for HIV-related lung diseases

Outcome variables

Mortality rate at one month after diagnosis of *P. carinii* pneumonia

Median survival from time of study entry

Median survival from estimated time of HIV infection using slope of decline in CD4 cells

Analysis

Appropriate regression models and nonparametric techniques will be used to address this question

Precision

Half-width 95% confidence interval on long-term mortality rate differences between "routine" and "intensively" screened groups is 6%.

Question 13. Does diagnosis of P. carinii pneumonia by intensive screening decrease number of days of hospitalization?

Groups studied

All HIV seropositive subjects

Predictive variables

Diagnosis by intensive or routine screening or by symptom evaluation

Confounding variables

Treatment regimens for P. carinii pneumonia

Coexisting diseases

Antiviral therapy

Preventive therapy for HIV-related lung diseases

Outcome variables

Days in hospital after PCP diagnosis

Analysis

These data will be analyzed using linear models.

Question 14. Does diagnoses of P. carinii pneumonia by intensive screening decrease the rate of deterioration in performance status?

Groups studied

All HIV seropositive subjects

Predictive variables

Diagnosis by intensive or routine screening or by symptom evaluation

Confounding variables

Treatment regimens for P. carinii pneumonia

Coexisting diseases

Antiviral therapy

Preventive therapy for HIV-related lung diseases

Outcome variables

Rate of decline in performance score

Analysis

These data will be analyzed using linear models.

Appendix 11

Protocol Changes

1. New Date of Protocol
2. Page 40, #10: "... or other qualified professional staff".

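### Appendix 1 makes the route of PCP diagnosis, not the randomised arm, the predictor for Questions 12–14, and two of the five outcomes are counted from diagnosis

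*Protocol*

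**What the plan says.** In Appendix 1, Questions 12 to 14 ask whether diagnosing PCP by intensive screening reduces mortality, hospital days and loss of performance status. For all three, the group studied is "All HIV seropositive subjects" and the predictor is "Diagnosis by intensive or routine screening or by symptom evaluation". The five listed outcomes have different time origins:

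| Question | Outcome | Counted from |
|---|---|---|
| 12 | "Mortality rate at one month after diagnosis of *P. carinii* pneumonia" | PCP diagnosis |
| 12 | "Median survival from time of study entry" | Study entry |
| 12 | Median survival, using the CD4 slope | Estimated HIV infection |
| 13 | "Days in hospital after PCP diagnosis" | PCP diagnosis |
| 14 | Rate of decline in performance score | Not stated |

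The precision entry for Question 12 is a 6% half-width for the difference in long-term mortality between the routinely and intensively screened groups.

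Section 9 treats Question 12 as a randomised comparison in which "the principal predictive variable of interest is intensive or routine screening and the outcome is short and long term mortality". It starts the survival curves at randomisation to avoid length-biased sampling, and allows estimated infection time as an additional start. It also says that the specific analysis plans are in Appendix 1 and that it discusses selected questions for illustration. Questions 13 and 14 are not among those.

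Section 7.2.3 has subjects analysed in the group to which they were assigned. Section 2, secondary objective 5, compares subjects whose disease was found through intensive screening or symptoms "with subjects who have had the same diseases diagnosed as a result of routine screening tests" or symptoms.

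**The concern.** The substudy of intensive against routine testing is the only randomised comparison in the protocol. Section 4 motivates it by noting that lead-time bias may explain the better survival seen in an earlier before-and-after comparison.

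The Appendix 1 predictor cannot be a shorthand for arm. It has three levels, and the third, symptom evaluation, occurs in both arms. It is undefined for anyone who never gets PCP. A subject must also survive to a PCP diagnosis to be classified at all. Grouping by it gives up the randomisation even for the survival outcomes that start at study entry.

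Where the outcome itself starts at diagnosis, a second problem is added. Screening can move the diagnosis earlier and can bring in milder cases, so the screened cases can look better with no death prevented.

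**Working it through.** **1. Which comparison does the 6% describe?**

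Inputs: three-year mortality of 15% in Group A and 50% in Group B (Appendix 3, note to the mortality tables); 527 subjects in each group, so 1,054 seropositive (Section 7.1.4, Table 5B); equal allocation (Section 5), so 527 per arm.

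- Pooled mortality: p = (0.15 + 0.50)/2 = 0.325.
- Half-width for the difference: 1.96 × √(2 × 0.325 × 0.675 / 527) = 0.0566, which rounds to the stated 6%.
- Half-width for one arm: 1.96 × √(0.325 × 0.675 / 527) = 0.040, as in Table 3.7.
- The transmission-category rows of Table 3.8 reproduce in the same way with 356, 136 and 35 per arm: 0.069, 0.111 and 0.219, against 0.07, 0.11 and 0.22.

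The precision statement therefore describes all seropositive subjects compared by randomised arm. It does not describe the predictor listed beside it.

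**2. How many subjects would have a value of the listed predictor?**

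Section 5 assumes AIDS-defining disease, mostly PCP, in 5% (A) and 20% (B) per year. Counting all of it as PCP over three years:

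- A: 527 × (1 − 0.95³) = 75
- B: 527 × (1 − 0.80³) = 257
- Total: 332, or 32% of 1,054; about 166 per arm

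With one-month mortality near 20%, the half-width for a difference between 166 and 166 cases is 1.96 × √(2 × 0.2 × 0.8 / 166) = 0.086, or 8.6 points. Section 6 expects PCP incidence to fall, so 332 is probably too high.

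**3. Lead time and one-month mortality (illustration)**

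Assumptions: 20% mortality (Section 3.3 gives about 20% for first episodes, with no 30-day window stated); deaths spread evenly over the 30 days after a symptomatic diagnosis; no true effect of screening; half of intensive-arm cases diagnosed L days early; 166 cases per arm. The lead time and the screen-detected share are not in the protocol.

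Apparent mortality in the intensive arm: q = 0.5 × 0.20 + 0.5 × 0.20 × (30 − L)/30.

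Chance of a nominally significant benefit: Φ(d/se − 1.96), with d = 0.20 − q and se = √(0.16/166 + q(1 − q)/166).

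| Lead L | Apparent mortality | Chance of false benefit (2.5% if unbiased) |
|---|---|---|
| 7 days | 17.7% | 8% |
| 14 days | 15.3% | 20% |
| 21 days | 13.0% | 41% |

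If every intensive-arm case had the lead, the figures would be 15.3%, 10.7% and 6.0%.

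**4. Over-diagnosis (illustration)**

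If screening adds a fraction e of non-fatal cases, apparent mortality is 0.20/(1 + e). For e of 10%, 25% and 50% this gives 18.2%, 16.0% and 13.3%, with a 6%, 17% and 42% chance of a false benefit.

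**The case against.** The strongest defence is that the protocol already contains the right analysis. Section 9 names the arms and the randomisation origin for Question 12. Section 7.2.3 is general and reaches Questions 13 and 14. Section 4 describes a comparison of a randomly selected subset with a routinely evaluated group. Appendix 1 itself takes all seropositive subjects as the population, quotes precision by arm, and says that it gives a general approach rather than an exhaustive list. This shows the intent, but it does not remove the conflict. Section 9 makes Appendix 1 the home of the specific plans, and the predictor line there is repeated in all three questions.

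Several stronger readings are tempting and are not supported:

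- A reader might infer that all outcomes in Questions 12 to 14 start at diagnosis. Two of five do. Lead time does not enter the two Question 12 survival outcomes through their origin, and Question 14 states none.
- A reader might infer that short-term mortality is planned only in a biased form. Section 9 puts it under the arm comparison. What is true is that the only definition of that outcome is the one in Appendix 1, counted from diagnosis.
- A reader might infer that objective 5 contrasts routes of diagnosis. Symptom evaluation appears on both sides, so it reads more naturally as arm among diagnosed cases. That is a different fault: it conditions on disease.
- A reader might infer that a false benefit is certain. Induced sputum is scheduled only at entry (Table 6), and in subjects without symptoms the scheduled visits trigger work-up by chest film (Section 7.2.4), so lead time may be short. For hospital days, earlier diagnosis can lengthen the period in which days are counted, which would work against intensive screening.

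**Conclusion.** The point holds in this form. The predictor that Appendix 1 lists for Questions 12 to 14 is a non-randomised variable that arises after randomisation and exists only for PCP cases. It contradicts Section 9 for Question 12, the as-assigned rule for all three questions, and the protocol's own 6% figure. Followed as written, it would discard the randomisation and classify at most about 332 of 1,054 subjects. That loss of denominator is a consequence of one repeated line, not of the plan as a whole.

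For one-month mortality the diagnosis origin can produce an apparent benefit of about 2 to 7 percentage points under the half-of-cases assumption. The size depends wholly on lead times and screen-detected shares that the protocol does not give. For hospital days neither size nor direction can be stated.

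This should be fixed but does not threaten the study: it is a secondary objective, and Section 6 accepts that failing to achieve it would not seriously reduce the study's value.

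**What to change.** In Appendix 1, Questions 12 to 14:

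- Set the predictor to randomised arm (A-1 plus B-1 versus A-2 plus B-2) in all randomised seropositive subjects, with time zero at randomisation.
- Question 12: all-cause mortality, short- and long-term, from randomisation, with the short-term horizon stated.
- Question 13: total hospital days per randomised person-year, zeros included.
- Question 14: slope of the performance score from randomisation.
- Label one-month mortality after PCP diagnosis, hospital days after diagnosis, and any comparison by route of diagnosis as descriptive only.

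Reword secondary objective 5, which compares diagnosed cases only, to match.

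One apparent compromise should be avoided: deaths within one month of a PCP diagnosis per randomised person-year. The denominator removes the dilution from over-diagnosis, but the window still starts at diagnosis. Under the even-spread assumption, a 14-day lead that saves nobody moves 14/30 = 47% of those deaths in screen-detected cases outside it.

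The cost is wording. Assignment is held by the Coordinating Center, performance status is scheduled for every group in Table 6, and hospital days are already an outcome for all seropositive subjects in Question 2. The 6% precision figure stands unchanged.

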The criteria used to classify patients will utilize the CDC Classification system published in the MMWR on May 23, 1986. This system is the most recent classification used by the CDC as well as other surveillance programs conducted by public health departments. Thus, using the CDC classification will be consistent with the terminology that future investigators will probably use. This classification is not intended for prognostic significance, but it is intended to be hierarchical. Those patients who are identified within a

particular CDC group cannot be reclassified into a preceding group if clinical findings resolve.

Admission lists for inpatients and appointment lists for outpatients in the clinic of the Infectious Disease Division will be reviewed daily to ascertain potential research subjects. Because appointment lists do not have diagnoses associated with names in order to protect patient confidentiality, the clerical support staff member will meet with the clinic physicians at the beginning of the clinic session to identify all known HIV seropositive cases. The clinic physicians are willing to recruit any HIV seropositive patient who is willing to participate. Patients under the age of 18 will be excluded in order to avoid the informed consent issues involved with minors.

In view of the anticipated recruitment for the study involving AIDS and alcohol, the investigators have available several lines of recruitment for this study. The American Red Cross, Wellness Networks, HFH staff physicians (480 group practice), substance abuse clinics, and gay organizations have been sources for the referrals to the AIDS clinic activities. These organizations have been faithful in their referral pattern and are committed to maintaining this relationship for the purpose of AIDS clinical research activities.

Northwestern University

Subjects will be recruited from the following sources:

- 1) After securing approval from the appropriate investigators, existing study cohorts will be reviewed to identify persons who are potentially eligible for the Pulmonary Complications of AIDS study;
- 2) Physicians at Northwestern known to be caring for significant numbers of HIV-infected persons will be contacted and asked to solicit interest in the study from the potentially eligible patients. Those patients who agree will have their names submitted to the PACS;
- 3) New patients presenting at the Northwestern HIV Care Center will be solicited for potential participation in PACS. Upon commencement of the study, the individuals identified from these groups will be contacted and asked to come to the study center where they will be assessed for participation in PACS;

- 4) Advertisements in a variety of local publications will be used to solicit participation in the study.

UCLA

Although it would be desirable to obtain a population based representative sample of HIV-infected adults in Los Angeles County, it will be difficult to ascertain if the sample is truly representative. Since a positive HIV test is not reportable, the available data on the number and demographic characteristics of HIV-infected individuals is based on the results of voluntary testing, and not necessarily representative of the entire population. In addition, the composition of the study population will be influenced by the feasibility of recruitment and follow-up of individuals in the different risk groups. For instance, although the prevalence of HIV infection among IV drug abusers and prostitutes may be increasing, many of these individuals will be difficult to recruit and maintain contact with over 4 years. We intend to aim our recruitment efforts primarily to homosexual and bisexual men, and to a lesser extent, intravenous drug abusers in methadone maintenance programs to attain the previously outlined target quota.

The degree to which the UCLA cohort is representative will depend on the ability of the investigators to contact individuals eligible for the study from as many sources as possible and to make participation as attractive as possible. Therefore we intend to: 1) maintain 3 clinics, each located and organized to provide maximum convenience and accessibility for the study participants; 2) name the study and clinics in such a way as to not disclose that they involve the study of HIV-infected persons; 3) establish a supportive relationship with each participant so that he feels he is benefiting from his role in the study; and 4) recruit from several sources.

Participants will be recruited from the following sources:

- A. Asymptomatic HIV-infected individuals and HIV seronegative controls.
 - 1) The current cohort of 1700 homosexual male subjects participating in the "Natural History of Acquired Immune Deficiency Syndrome in Homosexual Men Study;"

- 2) The "Alternative Testing Centers" which provide voluntary HIV testing located in West Hollywood, Long Beach, East Los Angeles, South Central Los Angeles, the San Fernando Valley, and the San Gabriel Valley;
 - 3) Gay events (e.g., the October Gay Health Fair) held by various gay men's associations;
 - 4) Methadone Maintenance Clinics participating in the Los Angeles County Drug Abuse Program for Methadone Treatment;
 - 5) Public service announcements and advertisements placed in local newspapers and magazines;
 - 6) Friends and acquaintances of participants enrolled in the study;
- B. Symptomatic HIV-infected Individuals
- 1) Symptomatic HIV-infected individuals seen in the outpatient facilities at UCLA Medical Center, LAC Olive View Medical Center and Wadsworth VA Hospital;
 - 2) The NIH funded UCLA AIDS Treatment Evaluation Unit (ATEU).

II. Recruitment of Study Participants

Brochures explaining the rationale and procedures of the study will be given to each participant of the "Natural History of Acquired Immune Deficiency Syndrome in Homosexual Men" study during routine visits. Posters will be displayed and brochures distributed at both Alternative Testing Centers and in the Methadone Maintenance Clinics. The posters, brochures, and public service announcements will briefly announce the study and give the study telephone numbers for more information and to set up an appointment at one of the two clinics. A booth is planned for Gay associations and participate as appropriate in other Gay events. Symptomatic HIV-infected individuals considered to be candidates for the study will be approached by the primary physician or ATEU physician during a clinic visit and given the study telephone number.

III. Retention of Study Participants

The incentive to volunteer for the study will be the examinations for the early detection of AIDS, or detection and diagnosis of associated lung disease. The results of the examination and tests will be provided to the physician designated by the participant (with his/her consent), as well as to the participant. The incentive for staying in the study will be the opportunity to receive periodic monitoring for early detection of AIDS or lung disease, up to date information on new treatment, etc. for HIV infection and complications, counseling for participants, family and friends and referral to various community resources.

